Appendix 3 Sponsor's Grading for Laboratory Values

Sponsor's Grading for Laboratory Values

	Grade 1	Grade 2	Grade 3	Grade 4
BLOOD/BONE MARROW				
Hemoglobin	<LLN – 10.0 g/dL <LLN – 100 g/L <LLN – 6.2 mmol/L	<10.0 – 8.0 g/dL <100 – 80 g/L <6.2 – 4.9 mmol/L	<8.0 g/dL <80 g/L <4.9 mmol/L; transfusion indicated	life-threatening consequences; urgent intervention indicated
Leukocytes (total WBC)	<LLN – $3.0 \times 10^9/L$ <LLN – 3000/mm ³	<3.0 – $2.0 \times 10^9/L$ <3000 – 2000/mm ³	<2.0 – $1.0 \times 10^9/L$ <2000 – 1000/mm ³	< $1.0 \times 10^9/L$ <1000/mm ³
Lymphocytes	<LLN – 800/mm ³ <LLN – $0.8 \times 10^9/L$	<800 – 500/mm ³ <0.8 – $0.5 \times 10^9/L$	<500 – 200/mm ³ <0.5 – $0.2 \times 10^9/L$	<200/mm ³ < $0.2 \times 10^9/L$
Neutrophils	<LLN – $1.5 \times 10^9/L$ <LLN – 1500/mm ³	<1.5 – $1.0 \times 10^9/L$ <1500 – 1000/mm ³	<1.0 – $0.5 \times 10^9/L$ <1000 – 500/mm ³	< $0.5 \times 10^9/L$ <500/mm ³
Platelets	<LLN – $75.0 \times 10^9/L$ <LLN – 75,000/mm ³	<75.0 – $50.0 \times 10^9/L$ <75,000 – 50,000/mm ³	<50.0 – $25.0 \times 10^9/L$ <50,000 – 25,000/mm ³	< $25.0 \times 10^9/L$ <25,000/mm ³
METABOLIC/LABORATORY				
Albumin, serum-low (hypoalbuminemia)	<LLN – 3 g/dL <LLN – 30 g/L	<3 – 2 g/dL <30 – 20 g/L	<2 g/dL <20 g/L	life-threatening consequences; urgent intervention indicated
Alkaline phosphatase	>ULN – 3.0×ULN	>3.0 – 5.0×ULN	>5.0 – 20.0×ULN	>20.0×ULN
ALT	>ULN – 3.0×ULN	>3.0 – 5.0×ULN	>5.0 – 20.0×ULN	>20.0×ULN
AST	>ULN – 3.0×ULN	>3.0 – 5.0×ULN	>5.0 – 20.0×ULN	>20.0×ULN
Bilirubin (hyperbilirubinemia)	>ULN – 1.5×ULN	>1.5 – 3.0×ULN	>3.0 – 10.0×ULN	>10.0×ULN
Calcium, serum-low (hypocalcemia)	<LLN – 8.0 mg/dL <LLN – 2.0 mmol/L	<8.0 – 7.0 mg/dL <2.0 – 1.75 mmol/L	<7.0 – 6.0 mg/dL <1.75 – 1.5 mmol/L	<6.0 mg/dL <1.5 mmol/L
Calcium, serum-high (hypercalcemia)	>ULN – 11.5 mg/dL >ULN – 2.9 mmol/L	>11.5 – 12.5 mg/dL >2.9 – 3.1 mmol/L	>12.5 – 13.5 mg/dL >3.1 – 3.4 mmol/L	>13.5 mg/dL >3.4 mmol/L
Cholesterol, serum-high (hypercholesterolemia)	>ULN – 300 mg/dL >ULN – 7.75 mmol/L	>300 – 400 mg/dL >7.75 – 10.34 mmol/L	>400 – 500 mg/dL >10.34 – 12.92 mmol/L	>500 mg/dL >12.92 mmol/L
Creatinine	>ULN – 1.5×ULN	>1.5 – 3.0×ULN	>3.0 – 6.0×ULN	>6.0×ULN
GGT (γ-glutamyl transpeptidase)	>ULN – 3.0×ULN	>3.0 – 5.0×ULN	>5.0 – 20.0×ULN	>20.0×ULN
Glucose, serum-high (hyperglycemia)	Fasting glucose value: >ULN – 160 mg/dL >ULN – 8.9 mmol/L	Fasting glucose value: >160 – 250 mg/dL >8.9 – 13.9 mmol/L	>250 – 500 mg/dL >13.9 – 27.8 mmol/L; hospitalization indicated	>500 mg/dL >27.8 mmol/L life-threatening consequences
Glucose, serum-low (hypoglycemia)	<LLN – 55 mg/dL <LLN – 3.0 mmol/L	<55 – 40 mg/dL <3.0 – 2.2 mmol/L	<40 – 30 mg/dL <2.2 – 1.7 mmol/L	<30 mg/dL <1.7 mmol/L life-threatening consequences; seizures

Sponsor's Grading for Laboratory Values

	Grade 1	Grade 2	Grade 3	Grade 4
Phosphate, serum-low (hypophosphatemia)	<LLN – 2.5 mg/dL <LLN – 0.8 mmol/L	<2.5 – 2.0 mg/dL <0.8 – 0.6 mmol/L	<2.0 – 1.0 mg/dL <0.6 – 0.3 mmol/L	<1.0 mg/dL <0.3 mmol/L life-threatening consequences
Potassium, serum-high (hyperkalemia)	>ULN – 5.5 mmol/L	>5.5 – 6.0 mmol/L	>6.0 – 7.0 mmol/L hospitalization indicated	>7.0 mmol/L life-threatening consequences
Potassium, serum-low (hypokalemia)	<LLN – 3.0 mmol/L	<LLN – 3.0 mmol/L; symptomatic; intervention indicated	<3.0 – 2.5 mmol/L hospitalization indicated	<2.5 mmol/L life-threatening consequences
Sodium, serum-high (hypernatremia)	>ULN – 150 mmol/L	>150 – 155 mmol/L	>155 – 160 mmol/L hospitalization indicated	>160 mmol/L life-threatening consequences
Sodium, serum-low (hyponatremia)	<LLN – 130 mmol/L	N/A	<130 – 120 mmol/L	<120 mmol/L life-threatening consequences
Triglyceride, serum-high (hypertriglyceridemia)	150 – 300 mg/dL 1.71 – 3.42 mmol/L	>300 – 500 mg/dL >3.42 – 5.7 mmol/L	>500 – 1000 mg/dL >5.7 – 11.4 mmol/L	>1000 mg/dL >11.4 mmol/L life-threatening consequences
Uric acid, serum-high (hyperuricemia)	>ULN – 10 mg/dL ≤0.59 mmol/L without physiologic consequences	N/A	>ULN – 10 mg/dL ≤0.59 mmol/L with physiologic consequences	>10 mg/dL >0.59 mmol/L life-threatening consequences

ALT = alanine aminotransferase (serum glutamic pyruvic transaminase), AST = aspartate aminotransferase (serum glutamic oxaloacetic transaminase), LLN = lower limit of normal, ULN = upper limit of normal, WBC = white blood cell.

Based on Common Terminology Criteria for Adverse events (CTCAE) Version 4.0. Published: May 28, 2009 (v4.03: June 14, 2010).

PROTOCOL SIGNATURE PAGE

Study Protocol Number: E2007-G000-311

## 2 LIST OF ABBREVIATIONS AND DEFINITIONS OF TERMS

Abbreviation	Term
ABNAS	A-B neuropsychological assessment schedule
AE(s)	adverse event(s)
AED	antiepileptic drug
ALT	alanine aminotransferase
AST	aspartate aminotransferase
ATC	anatomical therapeutic class
BMI	body mass index
CBCL	Child Behavior Checklist
CGI	Clinical Global Impression
CGIC	Clinical Global Impression of Change
CGIS	Clinical Global Impression of Severity
CRF	case report form
C ss,av	average steady-state drug concentration
C-SSRS	Columbia-Suicide Severity Rating Scale
DMC	Data Monitoring Committee
ECG	Electrocardiogram
EEG	Electroencephalogram
EQ-5D-Y	EuroQol 5 Dimensions – Youth
FAS	Full Analysis Set
LOCF	last observation carried forward
MedDRA	Medical Dictionary for Regulatory Activities
GTC	Generalized Tonic-Clonic
HRQL	health-related quality of life
ICF	informed consent form
IP	Investigational Products
LGPT	Lafayette Grooved Pegboard Test
LLN	lower limit of normal
LNH	low/normal/high
MedDRA	Medical Dictionary for Regulatory Activities

Abbreviation	Term
PD	Pharmacodynamics
PGTC	primary generalized tonic-clonic
PK	Pharmacokinetics
POS	partial-onset seizures
PT	preferred term
QTc	corrected QT interval (time from the beginning of the QRS complex to the end of the T wave, corrected for heart rate)
SAE	serious adverse event
SAP	statistical analysis plan
SI	Système International
SMQ	standardized MedDRA queries
SOC	system organ class
TEAE	treatment-emergent adverse event
TEMAV	treatment-emergent markedly abnormal laboratory values
TLG	tables, listings, and graphs
ULN	upper limit of normal
WHO	World Health Organization

### 3 INTRODUCTION

The purpose of this statistical analysis plan (SAP) is to describe the procedures and the statistical methods that will be used to analyze and report results for the core phase of Eisai Protocol E2007-G000-311. The statistical methods used in the extension phase will be described in a separate SAP.

#### 3.1 Study Objectives

##### 3.1.1 Primary Objective(s)

To evaluate the safety and tolerability of E2007/perampanel oral suspension when administered as an adjunctive therapy in children (ages 4 to <12 years) with inadequately controlled partial-onset seizures (POS) or primary generalized tonic-clonic seizures (PGTC)

##### 3.1.2 Secondary Objectives

1. To characterize the PK of perampanel and the relationship between perampanel plasma concentrations, efficacy, and safety using population PK/PD modeling
2. To evaluate the effects of perampanel on cognition, behavior, visuomotor skills, and growth and development in children during short-term (23 weeks) and long-term (up to 52 weeks) treatment
3. To evaluate the frequency of EEG abnormalities during awake and sleep state during 52 weeks of treatment
4. To evaluate suicidal ideation and suicidal behavior in children 6 years to less than 12 years as measured by the Columbia-Suicide Severity Rating Scale (C-SSRS) during 52 weeks of treatment
5. To evaluate the efficacy of perampanel as measured by the median percent change per 28 days in seizure frequency, by the proportion of responders ( $\geq 25\%$ ,  $\geq 50\%$ , and  $\geq 75\%$ ), and by the proportion of subjects who are seizure-free for POS, PGTC, and Generalized Tonic-Clonic (GTC) seizures
6. To evaluate, in Japanese subjects, the efficacy of perampanel on partial onset seizures (POS) in the present study as compared with placebo in Study E2007-J000-335
7. To assess the effects of perampanel on the Clinical Global Impression (CGI), CGI of Severity (CGIS) and CGI of Change (CGIC)

### 3.1.3 Exploratory Objective

To assess the impact of perampanel on the health utility of children using the Euroqol 5 Dimensions-Youth (EQ-5D-Y) scale.

## 3.2 Overall Study Design and Plan

This was a multicenter, open-label single-arm study in children (ages 4 to <12 years) with inadequately controlled POS or PGTC. The study was to consist of a Core Study and Extension Phase (Extension A, for all countries in the study) with an Additional Extension Phase (Extension B) available for subjects enrolled in Japan only. Subjects were to be stratified by age ( $\geq 4$  to <7 years, 7 to <12 years) with at least 30% subjects enrolled in the equal or greater than 4 to less than 7 year age group for each seizure type (ie, at least 36 with POS and at least 12 with PGTC).

### Core Study

The Core Study was to consist of the following 2 phases: Pretreatment and Treatment Phase. The Pretreatment Phase was to consist of a Screening/Baseline Period that lasts up to 4 weeks  $\pm 3$  days outside of Japan. Subjects in Japan were required to complete 4 full weeks  $\pm 3$  days of the Screening/Baseline Period. However, subjects outside of Japan could begin treatment as soon as baseline procedures were completed and documentation of eligibility (such as a documented seizure diary entry for a qualifying seizure during the preceding 12 weeks prior to Visit 2 or a qualifying seizure during the prospective Screening/Baseline Period) had been established. During this phase, subjects were to be assessed for eligibility to participate in the study.

The Treatment Phase was to consist of 3 periods: Titration (up to 11 weeks), Maintenance (up to 12 weeks), and Follow-up (4 weeks; only for those subjects not rolling over into the Extension Phase).

### Extension A

The Extension Phase was to consist of a Maintenance Period (29 weeks) and a Follow-up Period (up to 4 weeks; only for those subjects not entering into Extension B [Japan only]).

An overview of the study design is presented in [Figure 1 of the protocol](#).

### Extension B

Extension B was to be available to subjects enrolled in Japan and in countries where an EAP cannot be implemented. Extension B consisted of an open-label Treatment Phase. In Japan, treatment was continued as long as clinically appropriate according to the judgment of the investigator. However, treatment of subjects in Extension B was to be completed when the subject reaches 12 years of age or when perampanel is commercially available in Japan for treatment of POS in pediatric subjects (4 to less than 12 years of age). In countries where an EAP cannot be implemented, participation in Extension B was continued as long as clinically appropriate according to the judgment of the

investigator, until the subject reaches 12 years of age or perampanel oral suspension is commercially available. Subjects who discontinue or choose not to switch to the commercial product was required a Follow-up Visit which was to be conducted 4 weeks ( $\pm 7$  days) after the discontinuation Visit.

## 4 DETERMINATION OF SAMPLE SIZE

A sample size of 160 subjects (with up to 40 subjects with PGTC and the balance with POS), is deemed sufficient for safety evaluation in this age group (age 4 to <12 years). This sample size matches the total number of adolescents who were enrolled in the 4 global Phase 3 efficacy and safety studies that support the POS and PGTC indications.

For purposes of registration in Japan, it has been determined that a sample size of 65 subjects enrolled in Japan will provide 80% power to exclude the possibility that there would be a reduction smaller than that observed in the placebo arm of Study E2007-J000-335 (ie, 10.5%).

The sample size calculation was examined based on two scenarios of 10%, 40% and 50% or 10%, 30% and 60% of subjects receiving E2007 doses of 4mg, 8mg or 12mg respectively, as allocation group dose. In addition, the ratio of inducer medication user was assumed to be 70%. In either scenario, a sample size set 65 subjects is powered above 80%. The power is calculated from the number of counts from 10,000 re-sampling simulation about the upper limit of 95% confidence interval below 10.5%.

## 5 STATISTICAL METHODS

All descriptive statistics for continuous variables will be reported using mean, standard deviation (SD), median, minimum and maximum. Categorical variables will be summarized as number (percentage) of subjects. All summaries will be produced by age cohort (4-<7 and 7-<12), disease cohort (POS, PGTC, GTC) and inducer status (inducer, non-inducer) except TEAE summary by speed of titration. All analysis will be conducted for Japanese POS subjects in Japanese sites (Country=Japan).

### 5.1 Study Endpoints

#### 5.1.1 Primary Endpoints

Safety and tolerability, which include incidence of treatment-emergent adverse events (TEAEs) and SAEs, laboratory parameters, vital signs, and ECG parameters, of perampanel oral suspension in children (ages 4 to <7 years and  $\geq 7$  years to <12 years) with POS or PGTC

#### 5.1.2 Secondary Endpoints

The following endpoints will be analyzed:

1. The relationship between plasma levels of perampanel and efficacy endpoints (ie, change in average seizure frequency over 28 days, responder probability, and the proportion of subjects who are seizure-free in the Maintenance Period of the Core Study) separately for each seizure type
2. The relationship between plasma levels of perampanel and cognition endpoints including change from baselines in ABNAS, CBCL, and LGPT. In addition, depending on the AE data, the relationship between plasma levels of perampanel and select AEs will be assessed
3. Change from baseline at Week 23 and Week 52 in ABNAS, CBCL, and LGPT
4. Changes from baseline at Week 23 and Week 52 in growth and development parameters (height, weight, thyroid, and IGF-1)
5. Change from baseline in EEG and the frequency of EEG abnormalities during awake and sleep state
6. Proportion of subjects (aged 6 or older at time of consent/assent) with any treatment-emergent reports of suicidal ideation and behavior on the C-SSRS and intensity of these behaviors assessed using C-SSRS scores
7. The median percent change in seizure frequency per 28 days during Treatment Phase (Titration Period and Maintenance Period) of the Core Study, and during the long-term treatment (up to 52 weeks) relative to the Pretreatment Phase. Seizure frequency will be based on the number of seizures per 28 days, calculated as the number of seizures over the entire time interval divided by the number of days in the interval and multiplied by 28
8. Proportion of responders (25% responders defined as a decrease in 28-day seizure frequency of equal or greater than 25% compared to baseline seizure frequency; 50% responders defined as a decrease in 28-day seizure frequency of equal or greater than 50% compared to baseline seizure frequency; 75% responders defined as a decrease in 28-day seizure frequency of equal or greater than 75% compared to baseline seizure frequency) during Maintenance Period of Core Study, and during the long term treatment (up to 52 weeks)
9. Proportion of subjects who are seizure-free during Maintenance Period of Core Study, and during the long-term treatment (up to 52 weeks)
10. CGI of Change

### 5.1.3 Exploratory Endpoint

Change from baseline at Week 23 and Week 52 in EQ-5D-Y

## 5.2 Study Subjects

### 5.2.1 Definitions of Analysis Sets

The **Safety Analysis Set (SAS)** is the group of subjects who received at least 1 dose of study drug and had at least 1 postdose safety assessment.

The **Full Analysis Set (FAS)** is the group of subjects who received at least 1 dose of study drug and had at least 1 postdose primary efficacy measurement.

**PK Analysis Set** is the group of subjects receiving perampanel and with at least 1 quantifiable perampanel concentration at one of the visits during the Maintenance Period of the Core Study and with adequately documented dosing history.

**PK/PD Analysis Set** is the group of subjects receiving perampanel who have seizure frequency, cognition, or AE data with documented dosing history. Subjects receiving perampanel should have at least 1 quantifiable perampanel concentration at one of the visits during the Maintenance Period of the Core Study as per the PK Analysis Set.

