9.5.2 Schedule of Procedures/Assessments – Core Study

9.5.2.1 Schedule of Procedures/Assessments

[Table 4](#) presents the schedule of procedures/assessments for the Core Study.

Table 4 Schedule of Procedures/Assessments in Study E2007-G000-311: Core Study

Phase	Pre-Treatment	Treatment Phase									Early Discontinuation ^d	Unscheduled
	Screening/Baseline	Titration ^a				Maintenance ^b				Follow-up ^{b,c}		
Visit	1	2	3	4	5	6	7	8	9			
Week	From up to -4 weeks ±3 days to Week 0 (outside of Japan) -4 weeks ±3 days to Week 0 (Japan only) (revised per Amendment 02)	0	2	5	8	11	15	19	23	27		
Procedures/Assessments												
Demography	X											
Informed consent/assent	X											
Inclusion/exclusion criteria	X	X										
Medical history	X											
Epilepsy medical history	X											
Prior/concomitant medication(s)	X	X	X	X	X	X	X	X	X	X	X	X
Prior/concomitant AED(s)	X	X	X	X	X	X	X	X	X	X	X	X
Neurological examination ^e	X								X	X	X	
Physical examination ^e	X								X	X	X	
Vitals ^f and weight ^g	X	X	X	X	X	X	X	X	X	X	X	X
Height ^g		X							X		X	
Adverse events	X	X	X	X	X	X	X	X	X	X	X	X
Study drug compliance			X	X	X	X	X	X	X		X	X
Dispense study drug		X	X	X	X	X	X	X	X ^h			X ⁱ
Retrieve unused study drug			X	X	X	X	X	X	X		X	X ⁱ
Dispense subject's diary	X	X	X	X	X	X	X	X	X ^h			X
Retrieve and review diary		X	X	X	X	X	X	X	X	X	X	X
Clinical laboratory tests ^j	X ^k					X			X ^k	X	X	X

Table 4 Schedule of Procedures/Assessments in Study E2007-G000-311: Core Study

Phase	Pre-Treatment	Treatment Phase									Early Discontinuation ^d	Unscheduled
		Screening/Baseline	Titration ^a				Maintenance ^b			Follow-up ^{b,c}		
Visit	1	2	3	4	5	6	7	8	9			
Week	From up to -4 weeks ±3 days to Week 0 (outside of Japan) -4 weeks ±3 days to Week 0 (Japan only) (revised per Amendment 02)	0	2	5	8	11	15	19	23	27		
Procedures/Assessments												
Thyroid (TSH, fT3, fT4) and IGF-1 testing	X								X		X	
Serum β-hCG (or hCG) test ^l	X											
Urine pregnancy test ^l		X	X	X	X	X	X	X	X	X	X	X
C-SSRS ^m	X	X	X	X	X	X	X	X	X	X	X	X
12-lead ECG ⁿ	X								X	X	X	X ^o
EEG ^p	X								X		X	X ^o
Perampanel PK sampling (plasma) ^{q,r}							X	X	X		X	X
Telephone call ^s		X	X	X	X	X	X	X				
ABNAS ^t	X ^u	X					X		X		X ^v	
Lafayette Grooved Pegboard Test	X ^u	X					X		X		X ^v	
Child Behavior Checklist		X							X		X	
EQ-5D-Y		X							X		X	
Clinical Global Impression		X							X		X	
Disposition		X							X		X	
IxRS	X	X	X	X	X	X	X	X	X	X	X	X

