ABNAS = A-B neuropsychological assessment schedule, AE = adverse event, AED(s) = antiepileptic drug(s), β-hCG = beta-human chorionic gonadotropin (or hCG = human chorionic gonadotropin), C-SSRS = Columbia-Suicide Severity Rating Scale, eCRF = electronic case report form, EQ-5D-Y = EuroQol 5 Dimensions-Youth, fT3 = free triiodothyronine, fT4 = free thyroxine, IGF-1 = insulin-like growth factor-1, IxRS = interactive and response system, PK = pharmacokinetics, TSH = thyroid-stimulating hormone.

Table 4 Schedule of Procedures/Assessments in Study E2007-G000-311: Core Study

Phase	Pre-Treatment	Treatment Phase									Early Discontinuation ^d	Unscheduled
	Screening/Baseline	Titration ^a				Maintenance ^b				Follow-up ^{b,c}		
Visit	1	2	3	4	5	6	7	8	9			
Week	From up to -4 weeks ±3 days to Week 0 (outside of Japan) -4 weeks ±3 days to Week 0 (Japan only) (revised per Amendment 02)	0	2	5	8	11	15	19	23	27		
Procedures/Assessments												

- a: All visits to be done within ±3 days of the schedule. Each study visit is based on the actual prior visit (eg, Visit 3 is completed 2 weeks ±3 days of Visit 2, Visit 4 is completed 3 weeks ±3 days of Visit 3, Visit 5 is completed 3 weeks ±3 days of Visit 4). (revised per Amendment 02)
- b: Visit to be done within ±7 days of the schedule. Each study visit is based on the actual prior visit (eg, Visit 6 is completed 3 weeks ±7 days of Visit 5, Visit 7 is completed 4 weeks ±7 days of Visit 6, Visit 8 is completed 4 weeks ±7 days of Visit 7, Visit 9 is completed 4 weeks ±7 days of Visit 8). (revised per Amendments 02 and 03)
- c: The Follow-up Visit only applies to those subjects who complete the Core Study (or who discontinue the study early), but do not roll-over into Extension A and is to occur 4 weeks (±7 days) after Visit 9 or last dose of study drug.
- d: These assessments will be conducted for subjects who discontinue the study early for any reason after Visit 2.
- e: Physical and neurological examinations will only be performed at Visit 1 and Visit 9 and at the Follow-up Visit, and at the Early Discontinuation Visit (if applicable). For all other clinic visits during the study, the physical and the neurological exams will only be performed when there is a complaint from the subject. Clinically significant abnormal findings from the physical or the neurological examinations will be reported as AEs.
- f: Blood pressure and pulse will be taken.

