- g: Weight and Height (without shoes) will be measured. Three measurements should be taken at each visit. Each measurement should be recorded as a separate entry on the Vital Sign eCRF.
- h: Only for those subjects who continue into Extension A.
- i: Unused study drug to be retrieved and study drug dispensed only for subjects requiring dose increases at Unscheduled Visits.
- j: Clinical laboratory tests include hematology, blood chemistry including lipid panel, and urinalysis.
- k: Fasting lipid and glucose samples to be taken at baseline and at end of treatment or early discontinuation, with fasting window (interval) between 2 and 4 hours.
- l: Female subjects age 8 years old and above, or of childbearing potential, only. If urine can not be obtained for pregnancy testing after screening, a serum pregnancy test will be performed. (revised per Amendment 01)
- m: Only for subjects aged 6 years and older at the time of consent/assent.
- n: If subject has a normal ECG baseline reading, but during any visit thereafter, the QT is measured as greater than 450 ms, 3 consecutive ECGs separated by 5 to 10 minutes will be performed to confirm the abnormality.
- o: During Unscheduled Visits, ECG or EEG will only be done if the results from the previous visit were deemed clinically significant by the investigator.
- p: EEG will be performed at awake and sleep state for all subjects.
- q: One blood sample (approximately 1 mL) for determination of perampanel plasma concentrations will be collected at any time during each of the specified visits.

Table 4 Schedule of Procedures/Assessments in Study E2007-G000-311: Core Study

Phase	Pre-Treatment	Treatment Phase									Early Discontinuation ^d	Unscheduled
	Screening/Baseline	Titration ^a				Maintenance ^b				Follow-up ^{b,c}		
Visit	1	2	3	4	5	6	7	8	9			
Week	From up to -4 weeks ±3 days to Week 0 (outside of Japan) -4 weeks ±3 days to Week 0 (Japan only) (revised per Amendment 02)	0	2	5	8	11	15	19	23	27		
Procedures/Assessments												

- r: Additional blood (approximately 1 mL/sample) will be drawn at the 1st report (where possible) of a serious adverse event or severe unexpected AE and at its resolution. (revised per Amendment 01)

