9.7.1.7 Pharmacokinetic, Pharmacodynamic, Pharmacogenomic, and Other Biomarker Analyses

9.7.1.7.1 PHARMACOKINETIC ANALYSES

Pharmacokinetic Analysis

Population PK analysis will be performed to characterize the PK of perampanel by pooling the concentration data with other studies, including 19 Phase 1 studies, 2 Phase 2 studies (232 and 235), and 5 Phase 3 studies (304, 305, 306, 332, and 335). A 2-compartment PK model will be fit to the data and the effect of intrinsic and extrinsic factors, including body weight and age, on the PK of perampanel will be evaluated. The post-hoc estimates of both maximum observed concentration (C_{max}) and area under the curve (AUC) from the final PK model will be derived for all subjects. In addition, average steady-state drug concentration ($C_{ss,av}$) will be calculated. Subsequently, the dose-normalized derived exposure parameters will be summarized descriptively by age group (≤ 4 years, >4 to ≤ 8 years, >8 to <12 years, ≥ 12 to <18 years, and ≥ 18 years) for subjects with and without inducing AEDs, and also presented in box-plots.

Pharmacokinetic/Pharmacodynamic Analyses

Population PK/PD analysis will be conducted for the relationship between model-predicted average exposure to perampanel at steady-state ($C_{ss,av}$) vs responder rate and percent reduction in seizure frequency during the Maintenance Phase. In addition, the relationship between $C_{ss,av}$ and the cognition endpoints and most frequent AEs will be explored graphically. Any emergent relationship will be subjected to population PK/PD modeling. The effect of intrinsic and extrinsic factors (ie, most common concomitant AEDs, demographics) on the PK/PD relationship will be evaluated. Two separate analyses will be performed, one for POS, where data from subjects with POS from Study 311 will be pooled with data from POS subjects from Studies 304, 305, 306, and 335, and another for PGTC, where data from subjects with PGTC from Study 311 will be pooled with data from PGTC subjects from Study 332.

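### The PK and PK/PD sets require a Maintenance-visit concentration, so children who stop during Titration drop out of the exposure-AE analysis although PK blood is scheduled for them

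*SAP*

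**What the plan says.** **Set definitions.** SAP 5.2.1, with the same wording in protocol 9.7.1.2 and the synopsis, requires for the PK set "at least 1 quantifiable perampanel concentration at one of the visits during the Maintenance Period of the Core Study" plus an adequate dosing history. The PK/PD set covers children "who have seizure frequency, cognition, or AE data with documented dosing history" and repeats the Maintenance-visit condition.

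**Planned exposure-safety work.** Under secondary endpoint 2 (SAP 5.1.2), depending on the AE data, "the relationship between plasma levels of perampanel and select AEs will be assessed". Protocol 9.7.1.7.1 says that the relationship between model-predicted average steady-state concentration "and the cognition endpoints and most frequent AEs will be explored graphically", with modelling if a relationship emerges.

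**Sampling.** The PK row of protocol Table 4 is marked at Visits 7, 8 and 9 (Weeks 15, 19 and 23), Early Discontinuation and Unscheduled. Note d says of the Early Discontinuation column: "These assessments will be conducted for subjects who discontinue the study early for any reason after Visit 2". Note r adds blood that "will be drawn at the 1st report (where possible) of a serious adverse event or severe unexpected AE and at its resolution".

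**Methods.** SAP 5.5 leaves the population PK/PD methods to a separate analysis plan.

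**The concern.** One set serves two purposes. For exposure-efficacy, the Maintenance condition fits, because those endpoints are themselves measured in Maintenance. Exposure-AE is different: secondary endpoint 2 is not limited to Maintenance, and Titration is when the dose is raised step by step. A child who stops for intolerance during escalation is an AE case, and the set definition removes that child. Membership of the set then depends partly on the outcome being studied.

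At stake is secondary objective 1, which asks how plasma concentration relates to safety as well as efficacy. In addition, blood scheduled from young children under Table 4 would not count toward either set.

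**Working it through.** The plan states no figure for this point, so there is none to reproduce. The check is of the definitions against the schedule, followed by illustrative arithmetic.

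**1. Can a Titration drop-out qualify?** Routine PK samples start at Visit 7. For a child who stops in Titration, the only possible samples are Early Discontinuation, Unscheduled or event-driven ones. None is taken at a Maintenance visit, so the child fails both definitions. A child who stops in Maintenance before Week 15 qualifies only if the Early Discontinuation visit counts as a Maintenance visit, which is not stated.

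**2. How much of the Core Study is involved?** Titration is up to 11 weeks and Maintenance up to 12: 11/(11 + 12) = 11/23 = 47.8%. The first routine sample is at Week 15: 15/23 = 65.2% of the way through.

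**3. Effect on the AE rate.** Let N be the children treated, A those with a given AE, k the Titration drop-outs, and a the drop-outs with the AE. The rate in the restricted set is (A − a)/(N − k). It is below A/N only when a/k exceeds A/N, that is, when the AE is more common among drop-outs than overall.

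N = 160 is from SAP section 4. The drop-out rates, the 25% AE rate (A = 40) and the AE shares among drop-outs are assumptions.

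| Titration drop-out | k | N − k | 25% of drop-outs had the AE | 50% had it | 100% had it |
|---|---|---|---|---|---|
| 5% | 8 | 152 | 38/152 = 25.0% | 36/152 = 23.7% | 32/152 = 21.1% |
| 10% | 16 | 144 | 36/144 = 25.0% | 32/144 = 22.2% | 24/144 = 16.7% |
| 15% | 24 | 136 | 34/136 = 25.0% | 28/136 = 20.6% | 16/136 = 11.8% |
| 20% | 32 | 128 | 32/128 = 25.0% | 24/128 = 18.75% | 8/128 = 6.25% |

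**4. Effect on the slope.** For exposure x and retention R,

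logit P(AE | x, R) = logit P(AE | x) + log[P(R | AE, x) / P(R | no AE, x)].

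The last term decides the bias:
- If it does not vary with x, the slope is unchanged and only the rate moves.
- If it falls with x, because AE cases at higher exposure stop more often, the slope is flattened.
- If it rises with x, the slope is steepened. This can happen here. Table 1 escalates from 2 to 12 mg/day without an enzyme inducer and from 4 to 16 mg/day with one. A child who stops early stops at a low step, so the restriction can remove AE cases at low exposure.

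The documents do not say which applies.

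**5. Cognition.** ABNAS and LGPT at Early Discontinuation carry note v, which requires them only for children who stop after Week 12. Their first scheduled post-baseline assessment is Visit 7. Titration drop-outs therefore have no required post-baseline ABNAS or LGPT. Only CBCL is scheduled for them without that limit.

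**The case against.** The strongest reply is that the operative rules may lie elsewhere. The PK/PD methods sit in a plan that is not among the documents. No passage says outright that exposure-AE is run on the PK/PD set, and its concentration condition is worded as something children should have. This lowers confidence. It does not cancel a definition that names AE data and carries the Maintenance condition.

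Second, samples are not guaranteed. Protocol 9.5.1.4.1 describes routine sampling as a Maintenance activity and makes PK mandatory only at sites with trained staff and equipment. Event-driven samples are taken where possible, and 9.3.3 does not require the Early Discontinuation visit to take place on drug. This stands: some drop-outs cannot be recovered. It is no reason to exclude those who gave a sample.

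Third, the consequences are limited. Exposure-AE work depends on the AE data, starts as graphics, and pools this study with earlier ones, which dilutes the selection. That is fair, but pooling does not make this study's contribution representative.

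Fourth, the rule removes everyone who stops in Titration, not AE cases as such. Children with a Titration AE who continue are not excluded by this rule. This is correct, and it is why the understated rate is conditional on AE-driven stopping.

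A reader might also infer that the slope is flattened by a definite amount, or that the trial's safety results are biased. The documents support neither. Step 4 shows that the sign of the slope effect is open. SAP 5.6 runs the safety analyses on the Safety Analysis Set, which does not require a PK sample, and SAP 5.6.2 tabulates TEAEs leading to discontinuation.

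**Conclusion.** The point holds for the exposure-AE analysis. As defined, both sets exclude every child who stops in Titration, including those with a scheduled and quantifiable Early Discontinuation or event-driven sample. If the AE is more common among those children than overall, its rate in the set is too low. At an assumed 10% drop-out and a 25% AE rate, the shortfall is 2.8 percentage points (25.0 − 22.2) if half of them had the AE and 8.3 points (25.0 − 16.7) if all did. It is zero if only a quarter did. Slope bias is possible but of unknown direction and size, so no figure should be attached to it.

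The primary safety analysis is not affected, and the restriction suits exposure-efficacy. Confidence is moderate: the definitions and schedule are plain, but the separate PK/PD plan could specify a different set for exposure-AE.

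**What to change.** In SAP 5.2.1, protocol 9.7.1.2 with the synopsis, and the separate PK/PD plan:

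- For exposure-AE, and for the population PK estimates behind it, admit children with at least one quantifiable on-treatment Core Study concentration (scheduled, Unscheduled, event-driven or Early Discontinuation) and a documented dosing history. State how long after the last dose a sample still counts as on-treatment.
- Keep the Maintenance-visit requirement for exposure-efficacy, and use that set as a sensitivity set for exposure-AE.
- State which set each PK/PD analysis uses, and report how many children each set excludes and why.

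Do not expect much for exposure-cognition: only CBCL could gain.

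The cost is a change of definition, with no new samples or visits. Some added concentrations will not be at steady state, which the population model can handle through the dosing history. Not every drop-out will have a sample, so the exclusion will shrink but may not vanish.
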